3.6 VOM ETHANOL INFUSION AND PERIMITRAL FLUTTER (PMF)

Due to the frequent incidence of PMF, the difficulties in achieving perimitral bidirectional conduction block to treat it, and the potential risk of damaging the left circumflex coronary artery with RF ablation, there is a clinical need for new treatment strategies. We have evaluated the effect of VOM ethanol infusion on perimitral conduction in 43 patients (25 of which had PMF mapped prior to ethanol delivery). Although VOM ethanol infusion by itself only led to bidirectional perimitral block in 3 patients, this was easily achieved with minimal RF ablation in the most anterior aspect of the mitral isthmus (2.5 ± 1.3 min), anterior to the scar created by ethanol, in 98% of patients.¹⁰⁵ Figure 6 shows examples. Considering the low success rate reported by RF ablation (32%,⁵⁹ 64%,⁶⁰ or 71%⁶¹) –including epicardial ablation in the CS-, and the potential iatrogenic induction of recurrent flutters when bidirectional perimitral block is not achieved due to incomplete ablation, this novel technique promises to make a significant difference in the treatment of PMF.

Figure 6. PMF treated by VOM ethanol infusion

[figure not shown]
A, Example of PMF (counterclockwise, colors represent time). B, Conventional ablation sites (blue dots) in the mitral isthmus to treat PMF. C-F, Examples of ethanol-induced scar maps (voltage color scale) and locations of RF ablation lesions (arrowheads), required to achieve bidirectional mitral block.

3.7 ROLE OF VOM IN FAILED ABLATIONS

We have assessed the role of VOM activity in patients presenting for a repeat ablation procedure after a failed PVAI, as part of our R21 project. In 58 patients with recurrent AF, the VOM was cannulated in 51 and VOM signals were present in all of them, indicating that a *conventional PVAI procedure does not ablate VOM activity*. This was the case even in cases in which extensive LA ablation had been performed in the index procedure. [Figure 7](#) shows an example that illustrates that, even with extensive LA ablation (that caused most of the LA endocardium to be scarred –without detectable electrograms) the VOM remains electrically active.

Thus, as a novel catheter ablation technique, our preliminary mechanistic data in humans supports that VOM ethanol infusion provides rapid tissue ablation of targeted areas, helps treat PMF and achieves regional LA vagal denervation. The VOM is not otherwise ablated by conventional PVAI.

Figure 7. Lack of VOM ablation by PVAI

[figure not shown]
VOM. **C**, Fluoroscopic catheter position.

4.0 TRIAL OVERVIEW AND PRELIMINARY DATA

4.1 HYPOTHESIS

Our hypothesis is that a combined procedure of VOM ethanol infusion plus conventional PVAI (VOM-PV) is superior to PVAI alone in the catheter ablation treatment of persistent AF. We will compare the two treatments in a randomized fashion in 2 subsets of patients: *de novo* ablation, and repeat ablation in patients with persistent AF (Figure 8). Given the extent of tissue ablation required, we have chosen to use this technique in persistent AF, rather than in paroxysmal AF, in which less extensive tissue ablations may suffice. VOM ethanol infusion must be an add-on to the standard catheter ablation procedure, since it has no effect on other ablation targets such as the right PVs, septum, etc. Over our past experience we have established the safety of this procedure, uncovered novel mechanistic effects such as vagal denervation, and generated pilot data to support an improvement in outcomes.

Figure 8. Clinical Trial Design.

Commented [DE1]: Month 9 needs a description of what will happen at that time point

4.2 PRELIMINARY OUTCOMES DATA:

RESULTS OF OUR PILOT EXPERIENCE

We have compared our ablation outcomes in persistent AF patients treated with VOM-PV with those treated with PVAI. In 174 patients undergoing conventional PVAI, our single-procedure success rate at one year has been 45% (consistent with literature reports of 27%,⁴⁵ 36%,⁵⁷ or 49%⁵⁸). In contrast, in 66 patients with persistent AF subjected to VOM-PV, our success rate has been 61%. These data will be used for sample size statistical calculations for VENUS-AF, which enrolls a patient population undergoing their first AF ablation. Additionally, 62 patients with recurrent AF or flutter after a conventional ablation have undergone a repeat procedure including VOM-PV with a success rate of 76%. In our previous experience in such repeat procedures (n=169) our success rate was 42%, consistent with that of the literature.^{45, 57, 58} These data will be used for MARS-AF which enrolls a patient population undergoing repeat ablations.

1. For all patients:
 - a. Total procedure, RF ablation, and fluoroscopy times.
 - b. RF time and success of bidirectional block across the mitral isthmus line tested by differential pacing.
 - c. Pre-ablation 3D voltage maps.
 - d. Ablation lesion sets: 3D maps (Carto or NavX), including ablated scar surface area, as measured by bipolar voltage less than 0.1 mV.
 - e. Any procedural complications.
2. In patients randomized to VOM ethanol infusion:
 - a. Successful vs. unsuccessful cannulation with angioplasty wire and balloon.
 - b. Extent of tissue ablation achieved by ethanol infusion, defined as areas with local electrogram voltage <0.1 mV on 3D mapping. (Pre-PVAI voltage map).
 - c. Added procedural and fluoroscopy time.
 - d. Effect on AF: termination, conversion into flutter or no change.
 - e. RF time to achieve block around the mitral annulus.
 - f. Complications related to VOM instrumentation.
 - g. Blood ethanol level measurement.
 - h. LA instrumentation time.
 - i. Ablation lesion sets: 3D maps (Carto or NavX) including total (RF plus ethanol) ablated scar surface area, as measured by bipolar voltage less than 0.1 mV
 - j. Periprocedural data collection.

4.3 THREE MONTH BLANKING PERIOD

This protocol uses a three month “blanking period” as a period of time following an atrial fibrillation procedure in which atrial fibrillation episodes can occur as part of the body’s healing response. Any atrial fib/flutter activity during that blanking period is not counted in the study’s results and is not used in determining success or failure of the procedure as it is a common and expected outcome.

5.0 MATERIALS AND METHODS

5.1 SPECIFIC AIMS

Aim for VENUS is to assess the impact of VOM ethanol infusion in single-procedure success when added to de novo catheter ablation of persistent AF.

VOM triggers and innervation may play a role in persistent AF, and are not addressed by a standard PVAI. Our hypothesis is that VOM ethanol infusion will do so and lead to improved

outcomes. This is a prospective, multi-center, randomized study comparing a combined procedure including VOM ethanol infusion plus PVAI (VOM-PV) with PVAI alone in patients with persistent AF. The trial design incorporates a plan for possible repeat procedures if AF recurs after the 3-month blanking period, as this is common in clinical practice.

The aim of MARS is to assess the impact of VOM ethanol infusion after a failed conventional ablation of persistent AF.

Ablation failures requiring repeat procedures after PVAI are common, and can be due to recurrent AF, or new onset atrial flutters. We hypothesize that VOM ethanol infusion can be beneficial in these repeat procedures.

Our reported experience shows that VOM signals are uniformly intact in patients with recurrent AF after failed PVAI,¹ supporting the idea that VOM-dependent AF mechanisms are not addressed in conventional PVAI. Thus, we hypothesize that VOM ablation by ethanol infusion may have added value in this setting. Additionally, PVAI ablation failures may present as atrial flutters, including PMF and other circuits utilizing the mitral isthmus (e.g. reentry around the left PV antrum). We hypothesize, as supported by our recently reported data,³ that VOM ethanol infusion can assist achieving bidirectional mitral isthmus block by ablating most of the mitral isthmus and requiring minimal RF applications in the most anterior aspect of the isthmus (Figure 6). Patients with AF or flutter occurring beyond 3 months after a previous standard PVAI performed outside this study will be randomized to either a repeat PVAI procedure alone or a VOM-PV. The goal is to assess the role of VOM as an added salvage procedure to a repeat ablation. Heterogeneities in the index PVAI procedure are likely, but will be characterized in detail in the pre-procedure scar map using voltage mapping. Additionally, patients with recurrences as flutter are expected to have a greater success, so randomization will be stratified per flutter vs. AF recurrence.

5.2 STUDY ENDPOINTS

Primary endpoints:

1. Primary Efficacy Endpoint Freedom from AT/AF clinical recurrence on follow-up visits AND less than 30 seconds of AT/AF on a 1 month continuous electrocardiographic monitor at 6 and 12 months.
2. Primary Safety Endpoint - Acute procedural complications and total mortality.

Secondary Endpoints

1. Freedom from AF/AT after >1 procedure.
2. Freedom from AF/AT on antiarrhythmic drugs.
3. AF burden (% time) on continuous monitoring at 6 and 12 months.
4. Procedural parameters: total procedure, fluoroscopy, total RF ablation time (first procedure), and total extent of ablated LA tissue.
5. Clinical/partial success: less than 25% AF burden on a continuous event monitor at 6 and 12 months from ablation procedure.
6. Sub-acute procedural complications (within 30 days).
7. Recurrence as persistent or paroxysmal AF, or flutter after 1 or 2 procedures.

8. LA function on Doppler echocardiography (LA strain^{114ab}) at 12 months.
9. Incidence and mechanisms of atrial flutters.
10. Cardiovascular hospitalizations and
11. QOL as determined by AFEQT questionnaire.

5.3 INCLUSION AND EXCLUSION CRITERIA

Inclusion criteria

1. Patients between the ages of 21 and 85 years
2. Ablation History

Patients for **VENUS** must meet the following:

 - Diagnosed with symptomatic not previously ablated persistent AF,
 - AF not spontaneously converting to sinus rhythm, persisting for ≥ 7 days

Patients for **MARS** must meet the following

 - Recurrent AF or AT after a previous ablation of persistent AF at least 3 months prior to enrollment.
3. Resistant or intolerant to at least one class I, II, or III AAD
4. Patients deemed candidates for RF ablation of AF
5. Able and willing to comply with pre-, post-, and follow-up requirements.

Exclusion criteria

1. Left atrial thrombus.

LAA thrombus can be determined by pre-procedural imaging: CT, TEE or MRI. Documentation by exception (ie. no LAA thrombus on imaging reports) is permitted for determination of eligibility.
2. LA diameter greater than 65 mm on long axis parasternal view, or left atrial volume more than 200 cc.
3. Left ventricular ejection fraction < 30%.
4. Cardiac surgery within the previous 90 days.
5. Expecting cardiac transplantation or other cardiac surgery within 180 days.
6. Coronary PTCA/stenting within the previous 90 days.
7. Documented history of a thrombo-embolic event within the previous 90 days.
8. Diagnosed atrial myxoma.
9. Significant restrictive, constrictive, or chronic obstructive pulmonary disease with chronic symptoms.
10. Significant congenital anomaly or medical problem that in the opinion of the investigator would preclude enrollment
11. Women who are pregnant or who plan to become pregnant during the study.
12. Acute illness or active infection at time of index procedure documented by either pain, fever, drainage, positive culture and/or leukocytosis (WBC $> 11k/\text{mm}^3$) for which antibiotics have been or will be prescribed.
13. Creatinine $> 2.5 \text{ mg/dl}$ (or $> 221 \mu\text{mol/L}$, except for patients in dialysis).
14. Unstable angina.

15. Myocardial infarction within the previous 60 days.
16. History of blood clotting or bleeding abnormalities.
17. Contraindication to anticoagulation.
18. Life expectancy less than 1 year.
19. Uncontrolled heart failure.
20. Presence of an intramural thrombus, tumor, or other abnormality that precludes catheter introduction or positioning.
21. Presence of a condition that precludes vascular access.
22. INR greater than 3.5 within 24 hours of procedure – for patients taking warfarin.
23. Cannot be removed from antiarrhythmic drugs for reasons other than AF.
24. Unwilling or unable to provide informed consent.

5.4 INFORMED CONSENT PROCESS

The informed consent should be signed by the potential subject ***prior to any study-specific procedures taking place.***

An appropriately trained study team member will conduct the informed consent process with potential subjects in the approved manner for the institution, to include (at a minimum) the following procedures: ensuring the use of the most currently IRB approved document, allowing the potential subject sufficient time to read the consent and ask questions of the study staff, and ensure subjects have a clear understanding of the voluntary nature of their consent and the expectations for their commitment. The process above should be documented in the study record, apart from a copy being placed into the study file.

5.5 STUDY PROCEDURES

SCREENING/BASELINE

1. Initial assessment.

After signing informed consent, the following data will be collected; a significant medical history and recent targeted physical exam, electrocardiogram (EKG), echocardiogram within one year prior to the procedure for evaluation of cardiac structure, and function, and laboratory tests. In addition, a review of medications that patient is taking (limited to AAD and anticoagulants), and a quality of life (QOL) questionnaire especially developed for AF (AFEQT)¹¹³ will be filled out by patients.

Screening assessments performed pre-consent signature that are completed under standard of care can be included as viable source documents for patient study inclusion/exclusion and may be collected to screen potential study patients.

2. Pre-procedural imaging.

Imaging prior to enrollment is required to rule out structural heart disease and, as needed, to rule out the presence of LA appendage thrombus. *Ruling out LAA thrombus can be performed by the following: TEE, CT or MRI within 48 hours of the*

procedure; at least one month of oral anticoagulation prior to the procedure; or documented prior procedures of LAA occlusion or ligation. For ruling out structural heart disease, either a cardiac MRI, CT or transthoracic echocardiogram within 1 year prior to participation in the study is sufficient. Documentation by exception (ie. no LAA thrombus documented on imaging report) is permitted for determination of eligibility. Left atrial diameter and estimated left atrial volume will be obtained from any of these diagnostic modalities. There is no specific requirement for a pre-ablation CT or MR, since anatomical details of the LA can be obtained intra-procedurally with current mapping systems.

3 Randomization.

Randomization should take place after confirmation that all inclusion/exclusion criteria are met and measurements of LA volume are obtained. Patients will be randomized in a 1.15:1 fashion (to account for an 85% technical feasibility of the VOM procedure) to receive either VOM-PV or the conventional PVAI. Patients will be blinded to the randomization outcome.

PROCEDURE/DAY 0:

1 PVAI procedure

As part of a conventional catheter ablation of AF the following will be performed, all considered standard of care:

- a) Electrophysiological catheters will be inserted, including a CS catheter, a duodecapolar circumferential catheter, and an ablation catheter. The last two will be inserted in the LA via trans-septal punctures.
- b) Prior to ablation, geometry of the LA will be obtained using a 3-dimensional (3D) mapping system (any of the commercially available systems). This will generate a computerized geometry of the LA, including baseline voltage amplitudes in different regions. LA scar surface area (bipolar voltage less than 0.1 mV) will be collected.
- c) Lesion sets delivered by RF application will include, in a step-wise fashion, the following ablations, starting with PVAI and added sequentially per the operator's judgment if AF persists after each step is completed:
 - i) PVAI. RF should be applied 1 cm proximal to the PV ostia in a wide area circumferential pattern. Isolation will be verified by the absence of electrical activity from each PV and/or dissociated activity.
 - ii) The greater PV antra, including posterior wall and roof.
 - iii) Mitral isthmus: a line of RF ablation from the left inferior PV to the mitral annulus. Bidirectional block should be verified after completion by differential pacing.

- iv) Areas of complex, fractionated potentials.
- v) Sustained atrial flutters will be mapped and ablated as directed by the map and flutter location.
- vi) Following step 4c, if AF persists after all the RF ablations, the patient will be cardioverted to restore sinus rhythm. Given the potential variability of the extent of ablations, maps of the lesion sets (see below) will be collected and maintained in an imaging core laboratory.

2 VOM procedure

In patients randomized to VOM-PV, ***prior to the conventional PVAI***, the following will be performed:

- a) A 7F-9F sheath will be advanced in the CS via a right internal jugular vein access. Femoral vein access is also appropriate to cannulate the CS. Contrast injection in the CS will be performed via a sub-selector catheter (recommended 6F left internal mammary angiographic guide catheter) to identify the VOM. We will obtain a CS venogram and identify the location of the VOM. Cannulation of the VOM will be performed using the sub-selector catheter that can be torqued so that its tip is engaged in the ostium of the VOM. Contrast will be injected via the lumen of the sub-selector catheter to verify such engagement.
- b) If large enough, the VOM will be cannulated with an angioplasty wire (0.014") that will be advanced through the sub-selector catheter and into it. If the VOM is too small to accommodate the wire, venodilation with 200 µgm of nitroglycerine through the sub-selector catheter will be administered to facilitate VOM cannulation.
- c) An angioplasty balloon (1.5 -2 mm diameter, 6-8 mm length) will be advanced over the wire and positioned in the ostium of the VOM. The balloon will be inflated to occlude the vein. Contrast venograms of the VOM will be recorded in left and right anterior oblique projections. The angioplasty balloon will be then advanced as distally as possible in the VOM and the first ethanol injection will be performed there after balloon inflation. The balloon will be then deflated and retracted 1-2 cm for a repeat inflation and ethanol injection. Up to four, 1 cc injections (depending on the VOM length) of 98% ethanol will be delivered in the VOM by sequentially retracting the balloon up to the VOM ostium.
- d) The procedure will then continue with standard PVAI procedure as outlined in section 4.

3 Bipolar voltage amplitude maps to be performed:

Using an electro-anatomical mapping system, the extent of the scar –measured as bipolar voltage <0.1 mV- will be recorded:

- a. At baseline after gaining trans-septal access to the LA in both randomization

groups.

- b. After ethanol infusion, if randomized to VOM-PV.
- c. After completion of the PVAI ablation lesions, in both randomization groups.

5.6 POST-PROCEDURAL DATA COLLECTION:

Patients may receive follow-up standard of care procedures (ECG, physical exam, review of medical history and concomitant medications) at the study site or at a provider of their choice. If an investigator at a study site does not perform the visit, the study staff will have the patient sign a Release of Medical Information and request the applicable medical records from the patient's provider. All ECG tracings must be reviewed and interpreted by a study investigator. The AFEQT questionnaire may be conducted by telephone call with the patient.

- 1. Seven day telephone follow-up (+/- 3 days)** should be conducted by study coordinator to assess patient for symptoms of procedure related or disease related complications.
- 2. Thirty-day (30D) follow-up (+/- 10 days).** Follow up evaluation will include an EKG, assessment for complications including a targeted physical exam and a review of adverse events and concomitant medications (limited to AAD and anticoagulants) will be documented. Routine medications, including AAD may be continued. Symptomatic AF or flutter should be treated with AAD or cardioversion as needed but will not be recorded for endpoint assessment.
- 3. Three-month (90D) follow-up (+/- 30 days).** Evaluation will include an EKG, and assessment for complications, targeted physical exam and a review of adverse events and concomitant medications (limited to AAD and anticoagulants) will be documented. If the patient is in AF or flutter, a cardioversion will be performed electively within 2 weeks so that all patients are in sinus rhythm after the 3 month blanking period. AAD therapy will be discontinued in all patients at this time if they are clinically stable and in sinus rhythm.
- 4. Six-month (180D) follow-up up (+/- 60 days).** Follow up evaluation will include an EKG, and physical exam. Additionally, patients will fill out the AFEQT¹¹³ QOL questionnaire and will undergo a 3-4 week continuous EKG monitor (4 weeks if tolerated by patient) (see *Core laboratories*, below). Subjects who have a miniaturized, implantable rhythm recording device (such as Medtronic LinQ and others) or an implanted pacemaker/defibrillator may have the continuous rhythm data obtained from that device, and may forego the portable recorder. The purpose of this EKG monitor (4 weeks if tolerated by patient) is to screen for recurrent AF that may prompt an early repeat procedure. Patients that have clinical or EKG recurrences will undergo a PVAI procedure (see below and Figure 8).
- 5. Nine-month follow-up up (+/- 30 days).** Follow up evaluation will include an EKG and physical exam. Patients that have clinical or EKG recurrences will undergo a repeat PVAI procedure. The timing of a repeat procedure will be encouraged to be within 6 months of randomization.
- 6. Twelve-month follow-up up (+/- 60 days).** Follow up evaluation will include an EKG, and physical exam. Additionally, patients will fill out the AFEQT¹¹³ QOL questionnaire

and undergo a continuous EKG monitor (4 weeks if tolerated by patient) to determine the primary efficacy endpoint.

Subjects who have a miniaturized, implantable rhythm recording device (such as Medtronic LinQ and others) or an implantable pacemaker/defibrillator may have the continuous rhythm data obtained from that device, and may forego the portable recorder.

Patients will fill out the AFEQT¹¹³ QOL questionnaire. Additionally, echocardiographic assessment of LA function (LA ejection fraction, strain^{114ab}) will be performed by a central reader at Houston Methodist Hospital.

—

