5.7 VENUS: DEFINITIONS OF PROCEDURAL SUCCESS OR FAILURE AND INDICATIONS FOR REPEAT PROCEDURES

- 1. Success:** Freedom from AT/AF clinical recurrence on follow-up visits AND less than 30 seconds of AT/AF on a 1 month continuous electrocardiographic monitor .
- 2. Clinical Success.** Freedom from AT/AF clinical recurrence on follow-up visits but documented AF or flutter up to 25% of the time on a 1-month continuous electrocardiographic monitor. The rationale is to account for patients in whom a repeat procedure would not be clinically indicated, yet AF/AT would not be considered cured.
- 3. Repeat procedures. A repeat procedure will constitute an effectiveness failure for the purpose of the primary efficacy endpoint.** However, repeat procedures and their outcomes will be recorded for secondary outcome analysis. First, repeat procedures are a clinical reality in persistent AF, and a single-procedure success endpoint –does not capture it. Second, it is possible that VOM-PV on a first procedure may increase success of a second procedure –e. g. if the recurrences in VOM-PV group are as AT instead of AF. Both represent a clinical failure of the procedure, but a repeat procedure for AT is more likely to succeed.⁶⁵ Repeat procedures will be encouraged to be timed within the first 6 months of the randomization procedure. Although this may seem short, it is our clinical experience that the bulk of AF recurrences tend to occur shortly after the blanking period.¹¹⁵ Thus, we expect a minority of patients to recur late in this window.

Indications for a repeat procedure include:

- Procedure failure: Symptomatic, recurrent persistent AF or flutter detected clinically during the scheduled follow-up visits.
- Less than partial/clinical success: AF or flutter burden on electrocardiographic monitoring exceeding 25% regardless of symptoms. Monitoring will be performed at 6 months post randomization procedure.
- Symptomatic AF or flutter detected on electrocardiographic monitoring regardless of AF or flutter burden. Monitoring will be performed at 6 months post randomization procedure.

Data to be collected during a repeat procedure will include

- a. Documentation of PV isolation: number and location of reconnected PV at the baseline of the repeat procedure.
- b. Perimitral conduction: presence or absence of perimitral block.
- c. Mechanisms of atrial flutter, if present.
- d. Documentation of other RF ablation sites

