- e. Documentation of RF time, time to perimitral block (if not already achieved), fluoroscopy time, LA instrumentation time, and procedure time.
- f. Baseline and Final LA voltage map (using any commercially available electroanatomical mapping systems). Measurement of baseline and Final LA scar surface area.

4. Effectiveness (Treatment) Failures

Effectiveness failures towards the primary endpoint will include the following (see Figure 8):

- a. Clinical recurrence of AF or AT after 3-months.
- b. Documented AF or AT of 30 seconds or more on EKG monitor at obtained at 6 and 12 months.
- c. Requirement of a repeat ablation procedure for recurrent AT-AF.
- d. Death.

VENUS and MARS patients who have a recurrence after 3 months post randomization will have a repeat procedure (PVAI). Patients will be deemed to be effectiveness failure for the primary efficacy endpoint of the trial after repeat procedures. Still, subjects will:

- a. Remain in the study for the purpose of all secondary endpoints: these include quality of life, AF burden on event monitoring, success after multiple procedures.
- b. Undergo all clinically necessary procedures and treatments, including prescription of antiarrhythmic therapy and additional procedures needed to control atrial fibrillation or flutter. A crossover VOM procedure will be offered to those randomized to PVAI after 2 in-study procedures.
- c. Data on such additional procedures or treatment will be collected in the Electronic Data Capture system (EDC).
- d. An additional secondary endpoint will be created: total number of procedures performed and requirement of antiarrhythmic drugs.

5. VENUS: Cross-over of patients initially randomized to PVAI only.

If a VENUS patient is originally randomized to conventional PVAI and experiences a treatment failure after a repeat procedure he or she may undergo an additional conventional PVAI ablation procedure during the study. Crossover to VOM ethanol will only be allowed after 2 procedures are performed in the setting of study participation. This is allowed because certain recurrent flutters are particularly suited to respond to VOM ethanol. The primary and secondary endpoints will be computed following their original randomization group.

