- e. Documentation of RF time, time to perimetal block (if not already achieved), fluoroscopy time, LA instrumentation time, and procedure time.
- f. Baseline and Final LA voltage map (using any commercially available electroanatomical mapping systems). Measurement of baseline and Final LA scar surface area.

4. Effectiveness (Treatment) Failures

Effectiveness failures towards the primary endpoint will include the following (see Figure 8):

- e. Clinical recurrence of AF or AT after 3-months.
- f. Documented AF or AT of 30 seconds or more on EKG monitor at obtained at 6 and 12 months.
- g. Requirement of a repeat ablation procedure for recurrent AT-AF.
- h. Death.

Patients who have a recurrence after 3 months post randomization will have a repeat procedure (PVAI). Patients will be deemed to be effectiveness failure for the primary endpoint of the trial after repeat procedures. Still, subjects will:

- e. Remain in the study for the purpose of all secondary endpoints: these include quality of life, AF burden on event monitoring, success after multiple procedures.
- f. Undergo all clinically necessary procedures and treatments, including prescription of antiarrhythmic therapy and additional procedures needed to control atrial fibrillation or flutter. A crossover VOM procedure will be offered to those randomized to PVAI after 2 in-study procedures.
- g. Data on such additional procedures or treatment will be collected in the Electronic Data Capture system (EDC).
- h. An additional secondary endpoint will be created: total number of procedures performed and requirement of antiarrhythmic drugs.

5. Cross-over option for of patients initially randomized to PVAI only.

If a patient is originally randomized to conventional PVAI and experiences a treatment failure after a repeat procedure he or she may undergo an additional conventional PVAI ablation procedure during the study. Crossover to VOM ethanol will only be allowed after 2 procedures are performed in the setting of study participation. This is allowed because certain recurrent flutters are particularly suited to respond to VOM ethanol. The primary and secondary endpoints will be computed following their original randomization group.

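### Sections 5.6 to 5.8 conflict on whether a patient with asymptomatic, low-burden AF/AT seen only on the monitor has a repeat PVAI, and several secondary endpoints depend on the answer

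*Combined protocol and SAP*

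**What the plan says.** Four sentences are worded as requirements:

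- Section 5.6 item 4 (6-month visit): "Patients that have clinical or EKG recurrences will undergo a PVAI procedure (see below and Figure 8". This one refers the reader onward.
- Section 5.6 item 5 (9-month visit): "Patients that have clinical or EKG recurrences will undergo a repeat PVAI procedure". It has no cross-reference.
- Section 5.7 item 4: "VENUS and MARS patients who have a recurrence after 3 months post randomization will have a repeat procedure (PVAI".
- Section 5.8 item 4, for MARS: "Patients who have a recurrence after 3 months post randomization will have a repeat procedure (PVAI".

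Other text makes a repeat conditional. Item 3 of sections 5.7 and 5.8 lists three indications:

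- "Symptomatic, recurrent persistent AF or flutter detected clinically during the scheduled follow-up visits"
- "AF or flutter burden on electrocardiographic monitoring exceeding 25% regardless of symptoms"
- symptomatic AF or flutter on the monitor at any burden.

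Item 2 of both sections defines Clinical Success as no clinical recurrence at visits, with AF or flutter on the monitor for up to 25% of the time. It says the category exists for "patients in whom a repeat procedure would not be clinically indicated, yet AF/AT would not be considered cured". Footnote (e) of the schedule of events (section 7.1) permits repeats subject to criteria that it does not name.

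**The concern.** A site can follow either set of sentences and be compliant. Under one, a patient without symptoms who has brief or low-burden AF on the monitor is booked for a second ablation. Under the other, the same patient is a Clinical Success, for whom the protocol says a repeat is not indicated.

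Patients who have a repeat stay in the study for all secondary endpoints, so the choice carries into the results. It changes the count of procedures, who contributes to success after more than one procedure, and what the 12-month monitor measures (rhythm after one ablation or after two). It also bears on crossover: a PVAI patient may receive VOM ethanol only after two in-study procedures, so the rule for the second procedure helps decide who can reach that point. Sites that read the text differently add avoidable variation. Some patients may have an invasive procedure that another passage says is not indicated for them.

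**Working it through.** **Step 1. The plan's own figure.** VENUS states 91% power (0.909) for 0.56 versus 0.38 with 180 and 156 patients. Simulating the unpooled Z-test at 60/52, 120/104 and 180/156 with boundaries 3.953, 2.543 and 2.011 (400,000 runs) gives 0.910. The figure reproduces. The repeat rule could alter it only by changing who counts as a success.

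**Step 2. Does the rule change who is a primary success?** Under item 4 of sections 5.7 and 5.8, AF/AT of 30 seconds or more on the 6- or 12-month monitor is a failure, a clinical recurrence is a failure, and a repeat for recurrence is a failure. A patient with 30 seconds or more on the monitor is therefore a failure with or without a repeat. Primary result, sample size and power do not move.

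**Step 3. Where the texts agree and where they do not (recurrence after 3 months).**

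- Symptomatic persistent AF or flutter found at a visit: repeat under both.
- Burden above 25% on the 6-month monitor: repeat under both.
- Symptomatic AF or flutter on the 6-month monitor, any burden: repeat under both.
- No clinical recurrence, no symptoms, monitor AF/AT of 30 seconds or more and burden of 25% or less: repeat under 5.6 item 5 and item 4 of 5.7 and 5.8; not indicated under item 2 of 5.7 and 5.8. This is the firm conflict.
- Asymptomatic recurrence on the 9-month EKG: repeat under 5.6 item 5. It matches no listed indication, because the monitor-based indications refer to the 6-month recording. This case is unclear.

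**Step 4. Which endpoints depend on it.**

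- Total number of procedures: directly.
- Freedom from AF/AT after more than one procedure: through who has a second procedure.
- AF burden and clinical success at 12 months: both are measured after any earlier repeat.
- Crossover eligibility: through the two-procedure condition.
- First-procedure parameters (procedure, fluoroscopy and RF times): not affected.

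**Step 5. Scale.** The documents do not say how many recurrences are asymptomatic with burden of 25% or less. Only a ceiling follows from the planning rates:

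- VENUS failures: 180 × (1 − 0.56) = 79.2 and 156 × (1 − 0.38) = 96.7; total 175.9.
- MARS failures (37 and 32 patients): 37 × (1 − 0.76) = 8.9 and 32 × (1 − 0.42) = 18.6; total 27.4.

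Assuming that 10%, 30% or 50% of failures fall in the conflict group:

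- VENUS: 17.6, 52.8 or 88.0 patients.
- MARS: 2.7, 8.2 or 13.7 patients.

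These shares are assumptions. The totals also include failures first seen on the 12-month monitor, whereas the schedule of events marks repeats only at the 3-, 6- and 9-month visits.

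**The case against.** The best defence is that the protocol, read as a whole, treats repeats as conditional. Sections 5.7 and 5.8 are the ones whose titles promise indications for repeat procedures, while 5.6 is about data collection. Section 5.6 item 4 describes the 6-month monitor as a screen that may lead to a repeat, and it points onward. Section 5.1 speaks of possible repeats, footnote (e) is permissive, and the data table in section 6.0 names a page for evaluating a repeat. The item 4 sentences in 5.7 and 5.8 could also be read as fixing the type of repeat (PVAI, not VOM) rather than requiring one.

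Much of this stands, and it narrows the point. It does not remove it: the 9-month sentence and item 4 of 5.7 and 5.8 contain no reference to the indications, and item 2 describes patients with recorded AF for whom a repeat is not indicated.

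It is also fair that the indication list is introduced as inclusive. A reader might infer that every recurrence off the list contradicts the mandatory sentences. The text does not support that; the firm conflict rests on the Clinical Success definition. Figure 8 is not shown in the copy reviewed, so it may settle the matter or add to it.

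**Conclusion.** The inconsistency is real and should be corrected. It is confined to asymptomatic, monitor-only recurrence of at least 30 seconds and no more than 25% burden, with the asymptomatic 9-month EKG recurrence left unclear. It affects secondary endpoints and crossover eligibility. The primary endpoint, sample size and power stand. For the 9-month EKG case that assumes AF or AT on a visit EKG counts as a clinical recurrence at follow-up.

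Two stronger readings are tempting and not supported:

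- **That all planned VENUS failures, about 79 and 97, are affected.** They include clinical recurrences, high-burden AF and deaths, where the texts agree or do not apply. The pilot repeat rates in section 6.0 A (45% and 30%) do not size the group either, because their denominator is ambiguous and the rule behind them is not described.
- **That the effect must be unequal by arm because PVAI is expected to fail more often.** This needs the asymptomatic low-burden share in each arm, which is not given. Assumed shares of 37% in VOM-PV and 30% in PVAI give 0.37 × 79.2 = 29.3 and 0.30 × 96.7 = 29.0, which is no difference. Endpoints are computed by randomized group, so inconsistent application adds variation but does not by itself show bias.

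**What to change.** Reconcile section 5.6 items 4 and 5, items 2 to 4 of sections 5.7 and 5.8, and footnote (e) of the schedule of events, and check Figure 8 against the result, so that one repeat-procedure rule applies at every site. State explicitly how it treats asymptomatic monitor-only AF/AT of 25% burden or less and an asymptomatic EKG recurrence at 9 months. Which rule to adopt is a clinical decision for the investigators.

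Make sure the existing evaluation-for-repeat-procedure page records the indication for each repeat. The table in section 6.0 shows that it captures the type of recurrence but does not show whether it captures the indication. With that field, the secondary endpoints can be reported by indication.

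The cost is protocol wording, a short notice to sites and at most one data field. No change to sample size, boundaries or the primary analysis is needed.
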